EVITA

EVAluation of cardiac magnetic resonance Imaging (MRI) in follow up assessmenT of patients with pulmonary Arterial hypertension (PAH)
Prospective cohort study of *cardiac MRI in PAH*

STATISTICAL ANALYSIS PLAN

[name] / [name]

15th of December 2020

Sponsor: Centre Hospitalier Régional Universitaire de Nancy

Identifiers: NCT02845518 **Unique Protocol ID:** PHRC-15-0210

Principal Coordinator / Central Contact Person: [name] [name]

Methodologists and statisticians: [name] & [name]

I/ General considerations:

The 2-tailed significance level will set to $p < 0.05$.

II/ Descriptive analysis

Continuous variables will be expressed as mean \pm SD or as median (25-75 percentile) as appropriate. Categorical variables will be expressed as frequencies (percentages).

III/ Analyses to respond to main objective:

The aim of the trial is to assess the sensitivity and specificity cardiac magnetic resonance imaging (cMRI) regarding the diagnosis of hemodynamic criteria for intermediate risk or high-risk status determined from right heart catheterization (RHC) measurements. There will be 3 time-points: baseline, between 3 and 6 months and 24 months.

The outcome variable will consequently be hemodynamic criteria for intermediate risk or high-risk status defined as a cardiac index (CI) $< 2.5 \text{ l/min/m}^2$ or right atrial pressure $> \text{ or } = 8 \text{ mm Hg}$. This definition is in line with the last ESC/ERS guidelines for diagnosis and treatment of pulmonary hypertension (1).

The cMRI exposition variable will be defined as a cMRI CI $< 2.5 \text{ l/min/m}^2$ or a right ventricle ejection fraction (RVEF) $< 35\%$ or an absolute decrease of 10% of RVEF at a follow-up evaluation (for the second and third time-point).

Sensitivity, specificity and their exact 95% confidence intervals will be computed using the binomial distribution.

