However, by nature, 3 tests will be performed for each subject unless they experience death or are unable to perform one (or more) test during the follow-up. The repeated nature of the data will be considered including a random effect in the analyses. We will construct a logistic regression model with hemodynamic criteria for intermediate risk or high-risk status as outcome and cMRI dichotomous variable as exposure using a random effect at the patient level (2). The glmer command from the lme4 package will be used (R package, CRAN). Sensitivity and specificity and their confidence interval will then be extracted from the logistic model.

This analysis will consequently provide the overall (i.e. across the 3 time-points) sensitivity and specificity of cMRI integrated aforementioned exposition variable for the integrated aforementioned RHC definition taking into account the repeated nature of the data.

In addition, the following secondary analyses will be performed:

- sensitivity and specificity evaluation of cMRI integrated exposition variable for the integrated RHC at each time points (i.e. at baseline, 3-6 months and 24 months),
- sensitivity and specificity evaluation for each component of the RHC definition (i.e. considering only cardiac index $< 2.5 \text{ l/min/m}^2$ or only right atrial pressure $> \text{ or } = 8 \text{ mm Hg}$) and cMRI definition (i.e. considering only cMRI CI $< 2.5 \text{ l/min/m}^2$ or only RVEF $< 35\%$ or only absolute decrease of 10% of RVEF at a follow-up evaluation) overall and at each time-points.

In addition, parametric or non-parametric correlation analyses (depending on variable distributions) will also be performed for cMRI CI and RHC CI.

IV/ Analyses of Secondary objectives

Secondary objectives 1 and 2:

- 1) To assess the predictive value of the first occurrence of morbimortality events in 2 different analyses derived from RHC criteria (cardiac index (CI) $< 2.5 \text{ l/min/m}^2$ or a right atrial pressure $= \text{ or } > 8 \text{ mm Hg}$) and from cMRI criteria (CI $< 2.5 \text{ l/min/m}^2$ or RVEF $< 35\%$ or an absolute decrease of 10% of RVEF at a follow-up evaluation).
- 2) To assess the univariable association between first morbimortality events occurrence and NYHA functional class, 6-minute walk distance, plasma level of BNP/NT-proBNP, and continuous hemodynamic variables from cMRI, RHC and echocardiography data collected at baseline and after 3-6 months of follow-up.

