Internal validation of the multivariable model and of the score which could be derived from it will be performed using the bootstrap method described by Harrell *et al* (8). Importantly, variables will be used both as dichotomized variables (using the cut-offs used in the primary objective) and as continuous variables. In case a continuous variable should be dichotomized for lack of log-linearity, the cutpoint will be validated in the same bootstrap resamples as for the model and score. In addition, optimal cutpoints will also be assessed on the continuous variables based on C-index maximization (9).

Secondary objectives 4:

4) To quantify complications due to cMRI and to RHC.

This will be mostly a descriptive analysis. The overall frequency of reported adverse events and severe adverse events will be compared between groups using the Chi-Square test (or Fisher's exact test where requested). In addition, to account for the paired nature of the data, a McNemar test will be performed.

Secondary objectives 5:

5) To determine the magnitude of better tolerability of cMRI over RHC for the patient.

Physical and psychological distress due to cMRI and RHC will be measured with questionnaires.

The comparison of the Likert-type scales of the questionnaires will be carried out using the Chi-Square test.

Secondary objective 6:

6) To create a biobank for diagnosis and prognosis purposes This study is a prospective cohort study. PAH patients will be recruited in 20 centers of the French network of severe pulmonary hypertension.

Blood samples to obtain DNA at one visit from circulating blood cells and plasma at all visits with MRI.

References

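### Objective 5 asks how much better cMRI is tolerated than RHC, but its only named analysis is a Chi-Square test that ignores pairing and category order, with no paired effect or confidence interval

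*SAP*

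**What the plan says.** SAP section IV, under secondary objective 5, sets the aim as "To determine the magnitude of better tolerability of cMRI over RHC for the patient". On measurement it says: "Physical and psychological distress due to cMRI and RHC will be measured with questionnaires". On analysis it says only: "The comparison of the Likert-type scales of the questionnaires will be carried out using the Chi-Square test". It names no effect measure, confidence interval, paired method or ordinal method for this objective.

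Three other places bear on it:

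- Section IV, secondary objective 4, compares complications of the same two procedures. After a Chi-Square or Fisher test it adds: "In addition, to account for the paired nature of the data, a McNemar test will be performed".
- Section III has both procedures done in the same patients: one of its analyses is "sensitivity and specificity evaluation of cMRI integrated exposition variable for the integrated RHC at each time points".
- Section II reports categorical variables as counts with percentages.

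**The concern.** Each patient can rate both procedures, so the two sets of ratings are not independent samples. The Pearson Chi-Square test assumes that they are. It also treats the Likert levels as unlabelled categories, so it cannot distinguish a shift towards less distress from any other difference in shape. Finally, a test statistic does not estimate anything, whereas this objective is about a magnitude.

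Two things are at stake. A modest tolerability advantage of cMRI could be missed. And the report could reach its end with no properly calculated estimate of how many patients found cMRI easier, or by how much.

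**Working it through.** **Inputs.** From the SAP: one cohort, two procedures, Likert-type ratings, two-sided 0.05 (section I). The SAP gives no number of levels, sample size, correlation or expected difference for this objective, so there is no figure of its own to reproduce. The values below are assumptions: 5 levels (1 = least distress), 50 to 200 patients, within-patient correlation 0 to 0.7, shift 0 to 0.8 SD, one pair of ratings per patient.

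**Step 1: what the Chi-Square test sees.** Take 100 patients with cMRI ratings 40/25/20/10/5 and RHC ratings 25/25/25/15/10 over levels 1 to 5. With equal totals, chi-square = Σ(a−b)²/(a+b) = 225/65 + 0/50 + 25/45 + 25/25 + 25/15 = 3.46 + 0 + 0.56 + 1.00 + 1.67 = 6.68 on 4 df, p = 0.154. Shuffling the levels leaves this unchanged, and so does any re-pairing of the ratings.

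**Step 2: what it does not see.** Hold those two distributions fixed. The mean scores are 2.15 (cMRI) and 2.60 (RHC), a difference of 0.45 whatever the pairing. The share of patients who did better with cMRI does depend on the pairing:

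- Independent ratings: RHC worse 0.40×0.75 + 0.25×0.50 + 0.20×0.25 + 0.10×0.10 = 0.485; cMRI worse 0.25×0.25 + 0.20×0.50 + 0.10×0.75 + 0.05×0.90 = 0.2825; net 20 points.
- Correlation 0.5 (simulated): 0.458 − 0.204, net about 25 points.
- Perfectly aligned: 0.45 − 0, net 45 points.

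The precision of the 0.45 also changes. With independent ratings the variances are 6.05 − 2.15² = 1.4275 and 8.40 − 2.60² = 1.64, so the half-width is 1.96×√3.0675/10 = 0.34. Perfectly aligned, every difference is 0 or 1, the variance is 0.45×0.55 = 0.2475, and the half-width is 1.96×√0.2475/10 = 0.10.

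**Step 3: error rate and power.** Bivariate normal latent ratings were cut at the 20th, 40th, 60th and 80th percentiles, with 10,000 replicates per setting. For n = 100:

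| Correlation | Chi-Square type I error | Power at 0.3 SD: Chi-Square | Sign test | Signed-rank |
|---|---|---|---|---|
| 0 | 5.1% | 31% | 38% | 50% |
| 0.3 | 3.5% | 29% | 52% | 63% |
| 0.5 | 2.4% | 26% | 64% | 75% |
| 0.7 | 1.9% | 21% | 84% | 91% |

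The type I error of the paired tests was 3.1–3.9% (exact sign test) and 4.6–4.9% (signed-rank). At correlation 0 pairing carries no information, so the gap in that row comes from ignoring order; the widening below it comes from ignoring pairing.

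At correlation 0.5, power for Chi-Square / sign / signed-rank is:

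- 0.3 SD: 11/34/46% at n = 50 and 61/93/96% at n = 200.
- n = 100: 80/98/99% at 0.5 SD and 99.9/100/100% at 0.8 SD.

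A separate simulation with skewed categories (30/30/20/13/7%, 2,000 runs, n = 100, correlation 0.5, 0.3 SD) gave 26% for Chi-Square and 77% for signed-rank, so the result does not depend on equal category sizes.

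**Step 4: the estimate that is missing.** For n = 100, 0.3 SD and correlation 0.5 the mean difference is 0.40 levels. Its half-width is 1.96×SD(difference)/10 = 0.29 if paired and 1.96×√(var₁+var₂)/10 = 0.39 if treated as independent. At correlation 0.7 these are 0.23 and 0.39. In terms of patients, 44% rate RHC worse and 24% rate cMRI worse: a net 20 points, with half-width 1.96×√((0.44 + 0.24 − 0.20²)/100) = 1.96×0.08 = 16 points.

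**The case against.** **The McNemar sentence might cover it.** It stands under objective 4 and concerns adverse events. The standard form is for binary outcomes, and nothing extends it to the questionnaires. Its presence shows that the plan itself regards cMRI and RHC data as paired.

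**Section II already gives a magnitude.** In part this stands. Percentages per procedure show the direction and, with complete pairs, the difference in mean score. They give neither a confidence interval that respects pairing nor the share of patients who did better with cMRI (step 2).

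**The error is on the safe side.** This stands for one positively correlated pair per patient: the test under-rejects and will not manufacture a benefit, and for large differences it costs almost nothing. The SAP does not say what difference is expected, so the 0.3 SD case is illustrative. If ratings from three visits were pooled, the direction could reverse: with n = 100 the simulated type I error was 2.5% when all correlations were 0.5, and 11.6% with 0.3 between procedures and 0.7 within a procedure. The SAP does not say that visits are pooled, so this is a condition to guard against and not a charge.

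**The questionnaire is not shown.** Items, levels and visits may properly be left to the protocol. An item asking for a direct comparison of the two procedures would need no pairing argument. The wording reads most naturally as separate ratings of each procedure, so this limits what can be said about size but not about the method.

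**Conclusion.** The point holds: the analysis is wrong as written for this objective. The named test fits neither the paired design nor the ordered scale, and no planned quantity with a CI answers a question about magnitude. That conclusion rests on the text of the SAP, read as separate ratings of the two procedures by the same patients.

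The size rests wholly on assumed inputs. For a modest shift with moderate correlation, power falls to between about a third and two fifths of that of a paired ordinal test (26% against 75% and 64%); for a large shift the loss is negligible. The more important gap is the missing paired estimate. This is a secondary objective, and the sensitivity and specificity analysis and the Cox models do not depend on it. The change should be made, but it does not threaten the trial's main result.

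**What to change.** Replace the Chi-Square sentence under objective 5 with one named paired ordinal analysis and its matching effect with a 95% CI. Two forms are sound; the SAP should commit to one before the data are seen.

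- **Sign test**, reporting the share of patients who rate cMRI better than RHC minus the share who rate it worse. This assumes nothing about the spacing of the levels and answers the question in terms of patients, so it is a natural default.
- **Signed-rank test**, reporting a paired score difference. It has more power in the settings above, but it treats Likert steps as comparable distances.

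State which visit supplies the ratings. If ratings from more than one visit are combined, use a cumulative-logit mixed model with patient-level random effects for the intercept and for procedure, and report the procedure effect with its CI. Percentages per procedure can stay as description.

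The cost is a few lines of SAP wording and slightly different code. No new data are needed.
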